2.2.5 Analysis of the primary endpoint

The primary endpoint (TTOFS) was compared between the two treatment arms using a stratified two-sample log-rank test, with a $\alpha=0.05$ type I error, using stratification factors of age ≤ 39 vs. 40+ as defined for randomization. The test statistic and p-value were taken from the stratified Cox proportional hazards (PH) model (reported as score test). Hazard ratios (degarelix+letrozole /triptorelin+letrozole, so that $HR>1$ indicates increased hazard of event with degarelix+letrozole

and $HR < 1$ indicates decreased hazard of an event with degarelix+letrozole) were estimated from a stratified Cox PH model, with two-sided Wald 95% confidence intervals (CIs). Recall, here an event is a good thing, so we expect $HR > 1$.

Cox proportional hazards model were also used to assess the difference in time to optimal ovarian function suppression between the treatment arms adjusting for selected covariates including baseline E2 level, body mass index (BMI), smoking history, and recent oral contraceptive usage.

The distribution of the primary endpoint was summarized using the method of Kaplan-Meier with reporting of median TTOFS as well as cumulative probability of time to OFS (1- event-free probability). The standard errors used Greenwood's formula and the pointwise 95% CIs were obtained using complementary $\log(-\log(\text{endpoint}))$ transformation methodology.

Two-sided 95% confidence interval (CI) for the difference in proportion of patients who achieved optimal OFS (defined as E2 level ≤ 2.72 pg/mL or ≤ 10 pmol/L) between the two treatment arms at the end of the 1st, 2nd and 4th cycle were to be provided. *(Not performed due to all (except one data-point at end of cycle2) were at OFS by the end of cycle 1, not meaningful).*

Spider plots displayed the E2 data over scheduled sampling time. Boxplots illustrated the distribution of E2, FSH and LH at the scheduled sampling times.

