| PATIENT-REPORTED SYMPTOMS | 
The patient-reported symptoms (PRS) will be assessed using the Functional Assessment of Cancer Therapy Endocrine Subscale (FACT-ES) comprising 18 items (each has score range from 0 to 4) with a possible maximum total score of 72. Functional Assessment of Chronic Illness Therapy (FACIT) guidelines will be used for scoring and interpretation of the FACT-ES total score. Patients will be asked to complete a PRS Form at baseline (prior to randomization), at day 1 of cycle 2, at day 1 of cycle 4, and prior to surgery.
 
The objectives are:
 
 • To assess the differences in PRS score over time between the two treatment arms • To correlate the estradiol (E2) levels and total PRS score measured on day 1 of cycle 2 and day 1 of cycle 4 of triptorelin or degarelix administration • To summarize each of the 18 individual (endocrine symptom) items of the FACT-ES descriptively over time as the proportion of patients with “clinically significant” symptoms (those scoring 3 or 4) |
| STRATIFICATION | 
Stratification will be performed according to:
 
 • Age (in years): less than or equal to 39 versus 40 or more |
| STATISTICAL CONSIDERATIONS | 
To achieve the primary objective, E2 levels will be determined centrally from samples taken at day 1 of the first treatment cycle before the administration of the first dose of degarelix or triptorelin (baseline), and thereafter at 24 and 72 hours, 7 days and 14 days after the first injection, and on day 1 of cycles 2 to 6 before the administration of degarelix or triptorelin.
 
For sample size calculation, we assume that the cumulative percentages of patients in the triptorelin arm achieving optimal ovarian function suppression (defined as E2 ≤ 2.72 pg/mL or ≤ 10 pmol/L) will be 30% within 2 weeks, 60% within 4 weeks and 75% within 8 weeks, and that degarelix will provide more rapid suppression (i.e., 60% within 2 weeks, 95% within 4 weeks and 100% within 8 weeks). Enrollment of 25 patients in each treatment arm will provide at least 90% power to detect a difference in time to optimal ovarian function suppression between the two groups, using a two sample log-rank test with a two-sided significance level of 0.05.
 |

| | |
|----------------------------------|--|

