1.3 STATISTICAL DESIGN AND SAMPLE SIZE

50 patients will be randomized using 1:1 allocation and stratified based on age (≤ 39 vs. ≥ 40 years). to

- 25 patients to treatment with triptorelin plus letozole; and
- 25 patients to treatment with degarelix plus letozole.

The sample size was determined in consideration of the trial primary objectives. Specifically, the primary endpoint of time to optimal ovarian function suppression will be assessed in the two treatment arms and is defined as time from the first injection of degarelix or triptorelin to the first centrally assessed E2 ≤ 2.72 pg/mL or ≤ 10 pmol/L during the 6 cycles of neoadjuvant treatment. The blood samples are taken at day 1 of the first treatment cycle before the administration of the first dose of degarelix or triptorelin (baseline), and thereafter at 24 and 72 hours, 7 days and 14 days after the first injection, and on day 1 of cycles 2 to 6 before the administration of degarelix or triptorelin.

The following table provides the assumption on the cumulative percent of patients who are anticipated to reach optimal ovarian function suppression (E2 level ≤ 2.72 pg/mL or ≤ 10 pmol/L) during the 6 cycles of neoadjuvant treatment.

Treatment arms	Cumulative percent (%) of patients with E2 ≤ 2.72 pg/mL or ≤ 10 pmol/L				
	2 weeks	4 weeks	8 weeks	12 weeks	16 weeks
Triptorelin+Letrozole (control: arm A)	30	60	75	90	100
Degarelix+Letrozole (experiment: arm B)	60	95	100	100	100

With 23 patients in each treatment arm and based on the assumption in the table above, the study has 90% power to detect a difference in time to optimal ovarian function suppression (E2 ≤ 2.72 pg/mL or ≤ 10 pmol/L) between the two treatment arms, using a two-sample log-rank test at a two-sided significance level of 0.05. Calculations were performed using nQuery Advisor® (logrank test of survival in two groups, simulation with percentages specified in above table).

To allow for missing data, the study enrolls 25 patients to each treatment arm for a total of 50 patients.

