1.4 TRIAL CONDUCT

1.4.1 Protocol Versions/Amendments

The trial was activated with protocol version 1.0 on dated 28 March 2013, and first patient enrolled on 24 February 2014. Final patient enrolled in January 2017 with final enrollment of N=51.

There is no amendment.

1.4.2

IBCSG Data and Safety Monitoring Committee (DSMC) conducts regularly scheduled semi-annual reviews of interim clinical and safety data for trial 41-13 (TREND)

The DSMC conducted reviews on April 24, 2014 and subsequently around every 6 month, concluded the trial to continue as planned.

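### The primary HR, its CI and the p-value come from a continuous-time Cox model on events seen only at a few scheduled draws, with neither tie method nor time scale stated

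*SAP*

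**What the plan says.** The endpoint (SAP 2.2.3; Protocol 4.1) runs from the first injection to the first central estradiol assessment in the target range. Samples are drawn at baseline, "thereafter at 24 and 72 hours, 7 days and 14 days after the first injection, and on day 1 of cycles 2 to 6" (SAP 1.3), which gives nine post-baseline times.

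SAP 2.2.5 names an age-stratified log-rank test at 0.05. It then takes the test statistic and p-value from the stratified Cox model as a score test. The hazard ratios "were estimated from a stratified Cox PH model, with two-sided Wald 95% confidence intervals (CIs". A covariate-adjusted Cox model follows. No tie method, time scale or software is given for any of these fits. SAS is named only for the patient-reported symptom model (SAP 2.2.6).

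SAP 2.2.5 also drops the planned CI for the difference in proportions, because all but one data-point were at suppression by the end of cycle 1.

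On design, "50 patients will be randomized using 1:1 allocation", later "with final enrollment of N=51" (SAP 1.4.1). The power statement reads "With 23 patients in each treatment arm and based on the assumption in the table above, the study has 90% power", "using a two-sample log-rank test at a two-sided significance level of 0.05".

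**The concern.** The Cox partial likelihood is built for continuous event times. Here all events in an interval between draws are recorded at the draw that closes it, so many patients share one time. The ways of handling ties then stop agreeing. Breslow's approximation pulls the HR toward 1, Efron's does so less, and a grouped-time model treats the intervals as they are. The plan permits any of these, so its main effect estimate cannot be reproduced from its text.

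Two things raise the stakes. With the difference in proportions dropped, the Cox HR (unadjusted or adjusted) is the only between-arm effect estimate left for the primary endpoint. The p-value also comes from the Cox fit, and the score test with Breslow ties does not carry the variance correction that the log-rank test uses for tied data.

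**Working it through.** **Inputs.** Cumulative percentages suppressed at 2, 4, 8, 12 and 16 weeks (Protocol 15.1.1; SAP 1.3): triptorelin 30, 60, 75, 90, 100; degarelix 60, 95, 100, 100, 100. Two-sided 0.05; 23 per arm for power, 25 per arm planned.

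**1. The plan's own figure.** The stated method is "logrank test of survival in two groups, simulation with percentages specified in above table". Log-rank simulation at 23 per arm gives:
- events at the five table times: 92.8%
- full draw schedule: 91.2% unstratified, 90.0% age-stratified (two equal strata and constant hazard within intervals assumed).

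Schoenfeld's formula with 46 events and HR 2.57 gives √(46/4) × ln 2.57 − 1.96 = 1.24, or 89.2%. The stated 90% reproduces.

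**2. Hazard ratios implied by the table.** Ratio of log conditional survival, degarelix over triptorelin:
- weeks 0–2: ln 0.40 / ln 0.70 = 2.57
- weeks 2–4: ln(0.05/0.40) / ln(0.40/0.70) = 3.72
- weeks 4–8: infinite, since the rest of the degarelix arm responds.

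The table is not proportional, so it has no single true HR.

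**3. Breslow estimate by hand.** Take 20 per arm to get whole numbers. Events are 6, 6, 3, 3, 2 (triptorelin) and 12, 7, 1, 0, 0 (degarelix). Numbers at risk are 20, 14, 8, 5, 2 and 20, 8, 1, 0, 0. The Breslow HR r solves Σ d·n₁r/(n₁r + n₀) = 20, the degarelix total. At r = 2.069:
- 18 × 41.38/61.38 = 12.135
- 13 × 16.552/30.552 = 7.043
- 4 × 2.069/10.069 = 0.822

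These sum to 20.00, so the HR is 2.07. A grouped-time (complementary log-log) fit to the same counts gives 3.18.

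**4. Table scenario on nominal days (large-sample values).**

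| Event times | Breslow | Efron | Grouped-time |
|---|---|---|---|
| Five table times | 2.07 | 2.93 | 3.18 |
| Full draw schedule | 2.25 | 2.96 | 3.17 |

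Simulated medians at 25 per arm on the full schedule: Breslow 2.27–2.32, Efron 2.92–2.94 (2.84 with two age strata), grouped-time 3.37–3.43. Cox on the underlying continuous times gave 3.11–3.35, so grouped-time runs slightly high in small samples.

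**5. True proportional hazards, nominal days, 25 per arm.** For true HR 2, 3 and 4:
- Breslow: 1.71, 2.31, 2.87, so 1 − 1.71/2 = 15%, 23% and 28% short. Two other runs gave 1.67, 2.33, 2.70 and 1.73, 2.28, 2.80.
- Efron: 1.94, 2.90, 3.48, so 3%, 3% and 13% short; a repeat gave 3–12%.
- Grouped-time: 2.07, 3.24, 4.07.

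**6. Actual dates spread by −1 to +2 days (assumption), table scenario.** Three runs gave Breslow medians of 2.67, 2.63 and 2.59. The first two compare with 3.11 and 3.13 on the underlying times (14% and 16% short). The third is 1 − 2.59/3.2 = 19% below the low end of the grouped-time range. Under proportional hazards of 2.57 and 3.18 the same spread gave 2.29 and 2.74, or 11% and 14% short.

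**7. The score test.** With the counts in step 3 and HR = 1, expected degarelix events are 9 + 4.727 + 0.444 = 14.17, so O − E = 5.83.
- Breslow variance Σ d·p(1−p) = 4.5 + 3.008 + 0.395 = 7.90; chi-square 4.30.
- Log-rank variance multiplies each term by (n−d)/(n−1), that is 22/39, 9/21 and 5/8: 2.538 + 1.289 + 0.247 = 4.07; chi-square 8.34.

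Simulated power of the Breslow score test at 23 per arm is about 66% at the table times and 75–77% on the full schedule, against 90–93% for the log-rank test.

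**The case against.** **Breslow is not documented.** A reader might infer that the SAS default was used, because the SAP names SAS. It does so only for the symptom model, and Efron would be only modestly short. This stands: the documents show an unspecified rule, not a demonstrated bias.

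**The size depends on nominal days.** A reader might infer that the HR must fall a quarter to a third short and below every interval HR in the table. The first does not hold throughout: at a true HR of 2 the shortfall is about 15%. The second needs every draw on its nominal day. SAP 3.6 tabulates off-schedule draws, and with the assumed date spread Breslow gives 2.59–2.67, no longer below 2.57. This also stands, and is why the time scale must be stated.

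**Ties are lighter early on than the table suggests.** The 30% and 60% at two weeks are spread over four draws. With constant hazard, the largest single-draw risks in that period are 1 − √0.70 = 16% and 1 − √0.40 = 37%, at day 14. Only the week-4 risks, 30/70 = 43% and 35/40 = 88%, fall at one draw. The full-schedule figures already allow for this.

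**The table is a poor proxy for the data.** It assumed "30% within 2 weeks, 60% within 4 weeks and 75% within 8 weeks" (Protocol 1) on triptorelin, whereas almost all patients were suppressed by the end of cycle 1. The real effect of ties could be smaller or larger. With an assumed faster control curve (10, 25, 60 and 97% by days 3, 7, 14 and 28) and a true HR of 3, Breslow gave 2.02, Efron 2.49 and grouped-time 3.21.

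**Other summaries exist, and attenuation is conservative for degarelix.** Medians and Kaplan-Meier probabilities are reported, but per arm. Conservatism does not make an estimate of how much faster degarelix works accurate.

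**Conclusion.** The concern holds as a gap in specification with material consequences. Choices that the plan leaves open move the table-scenario HR from about 2.1–2.3 (Breslow) to 2.9–3.0 (Efron) or 3.2–3.4 (grouped-time), all on nominal days.

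These figures rest on the planning table or on assumed proportional hazards, on constant hazard within intervals for the full schedule, and on nominal draw days except where a date spread is stated. They do not measure the error in the HR that was reported.

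Nor would it be right to infer that only the effect size is affected. The p-value comes from the same fit, and with Breslow ties its power would fall below the stated 90%.

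**What to change.** In SAP 2.2.5:

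1. Define event time by the scheduled draw.
2. Estimate the HR with a method suited to ties: a grouped-time proportional hazards model (complementary log-log link, one intercept per draw interval) or exact ties; Efron at minimum. Stratify by age and give a profile-likelihood 95% CI.
3. Use the same method for the covariate-adjusted model.
4. Take the primary p-value from the stratified log-rank test with its usual tied-data variance, not from a Breslow Cox score test. The SAP already names the log-rank test, so this clarifies the plan.

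The cost is a few sentences and a small rerun, with no new data. The drawback is that the grouped-time estimate runs slightly high at this sample size (3.24 for a true HR of 3).

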2.2.6 Analyses of secondary endpoints

- Node negative disease at surgery: The percentage of patients with node-negative disease at surgery will be descriptively summarized by treatment arm. Two sided 90% CI for the difference in percentage of patients with node-negative disease between treatment arms will be reported.
- Breast-conserving surgery (BCS):
 - Details of the surgical procedure performed overall and according to treatment arms.
 - The percent of patients in each treatment arm who had a breast-conserving surgery were presented, and the difference between the treatment arms were assessed using a two-sided exact 90% CI.
 - Rate of conversion (patient identified as candidates/planned for BCS or mastectomy per data on RA-form vs surgery performed on C-form): Cross-tabulation of surgery status between “planned” vs ‘performed’ and the percent in conversion overall and according to treatment arms were presented.
- Change in Ki67 (Surgery population, unless otherwise noted)
 - Ki67 expressions at baseline (pre-treatment, based on ITT population) and at surgery were descriptively summarized (median, IQR and mean) according to treatment arms.
 - The change in Ki67 expression from baseline (pre-treatment) to surgery was summarized for each treatment arm and two-sided 90% CI for the change were calculated and explored using a paired sample Wilcoxon signed-rank test.

- The percentage changes in Ki67 expression between the treatment arms from baseline to surgery were assessed using a two-sided 90% CI and explored using a two-sample Wilcoxon rank sum test.
- Boxplots were used to illustrate the marker distribution at baseline and surgery timepoints.
- Spider plots were used to show the individual paired Ki67 data from baseline to surgery.
- The preoperative endocrine prognostic index (PEPI) score at time of surgery
Patients in surgery population will be included in the assessment. Descriptive statistics are used to summarize the PEPI score by treatment arm. Two-sided 90% CI for the difference in the PEPI scores between the two arms maybe constructed. (*NOT DONE, given only one pt had PEPI score of 0*)
- Objective response was defined as CR/PR vs. Others (SD/PD/NE), where NE stands for non-evaluable:
 - Best overall response, overall and by treatment arm, were provided with Ns and proportions.
 - Objective response (CR/PR as best overall response) rate was summarized as N (%) with 90% CI, overall and by treatment arm, as well as the absolute percent difference of objective responses between arms were reported with exact binominal 90%CI.
 - Clinical responses at the end of cycle 3 and 6, including complete response (CR), partial response (PR), stable disease (SD) and progressive disease (PD) were descriptively summarized by treatment arms.
- Safety and tolerability

Tolerability was evaluated in each treatment arm separately, using the safety population. For each patient, the targeted AEs recorded over time were summarized for each AE type as the maximum grade reported for that AE (without regard to reported relation to study treatments). The frequencies and percentages of patients experiencing each targeted AE were reported according to maximum grade, separately by treatment arm.. Two-sided 90% exact confidence interval (CI) for the difference in proportion of patients with each type of grade 3 or higher targeted AE between the treatment arms were assessed.

- The maximum grade of all targeted AEs are summarized by treatment arm, and the number and percentage of patients experiencing at least one grade 3 or higher targeted AE will be reported (with CI) according to treatment arm.
- Targeted adverse events (AEs) and other (non-targeted) grade 3 or higher AEs occurring during study were collected using CTCAE v4.0 on the AE Form. The AE Forms were submitted at the end of every cycle (27 days) and 30 days after surgery. All patients submitted AE data during 6 cycles of treatment period when available.
- AEs are reported as maximum grade. The maximum grade consolidates the reports of a given type of AE for a patient over time by taking the maximum

(worst grade) across time (i.e., a patient appears only once for a given type of AE). Patients with reports of multiple AEs of different types are reported multiple times under the relevant AE categories. Maximum grade 0 indicates that the AE type was not reported.

▪ Patient-reported symptoms (PRS) analysis

Longitudinal assessments collected PRS outcome at *baseline* (prior to randomization), at *day 1 of cycle 2 (day 29)*, at *day 1 of cycle 4 (day 85)* of triptorelin or degarelix administration and prior to surgery.

The PRS were assessed using the Functional Assessment of Cancer Therapy Endocrine Subscale (FACT-ES: for endocrine symptom) comprising 19 items (each has score range from 0 to 4) with a possible maximum total score (denoted as ESS) of 76. Functional Assessment of Chronic Illness Therapy (FACIT) guidelines will be used for scoring and interpretation of the FACT-ES total score.

The primary endpoint was FACT-ES total score (or ESS). Note that the FACT-ES items are negatively framed, thus scores were reversed for analysis so that high scores equate to a good quality of life (QOL) [Lesley et al]

In order to better describe the specific type of QOL measures, as exploratory analysis, four subscales/groups of FACT-ES were also summarized, namely,

- Vasomotor symptoms (VS, score 0-12): hot flashes, cold sweats, night sweat (note: sleeping difficult was an item not collected in our dataset)
- Neuropsychological symptoms (NS, score 0-16): light-headed/dizzy, headache, mood swings, feeling irritable (lack of energy, nervous were not collected in our study)
- GI symptoms (GIS, score 0-16): Vomiting, Gained weight, Diarrhea, bloated feeling (nausea no data)
- Gynecologic symptoms (GYNS, score 0-28): vaginal discharge, vaginal irritation, vaginal bleeding, vaginal dryness, discomfort intercourse, lost interest in sex, breast tenderness

To provide clinically useful information regarding treatment side effects, patient responses to each ES question are labeled as “clinically significant” if they scored 3 or 4 (corresponding to “quite a bit” or “very much” a problem, respectively, on the questionnaire) and as “not clinically significant” for scores of 0, 1, or 2 (“not at all”, “a little bit”, or “somewhat” a problem, respectively). The questionnaire is completed before any subsequent procedures or treatment and refers to the past 7 days.

All patients who received at least one dose of study treatment and with at least one FACT-ES assessment were included in the analysis (PRS population=ITT population).

The differences in FACT-ES scores (ESS) measurements between the two treatment arms over time were assessed using a mixed-effect model (SAS proc mixed, note a change from GEE model stated in the protocol, due to the small sample size and for simplicity). The ESS

scores as well as the 4 subscales and individual FACT-ES items were modeled as a function of time and treatment arm to investigate the time pattern of FACT-ES scores and differences controlling for the stratification factor of age (dichotomized ≤ 39 vs $40+$ years). The covariance structure used *autoregressive* (type =AR(1) assuming between observations on the same patient are not equal but decrease toward zero with increasing lag). All available data were included in the model.

This model described the effects of two neoadjuvant treatments (degarelix+letrozole or triptorelin+letrozole) on FACT-ES for the observation period. The analysis will be exploratory, given the limited sample size (maximum 25 patients per treatment arm). The power of the repeated measure test is likely to be low except if treatment differences are substantial.

Means scores at each timepoint for each treatment arm, and for the difference between the treatment arms, were estimated from the models and reported with 90% CIs.

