6.1. Criteria for patient eligibility

- 6.1.1. Female gender
- 6.1.2. Premenopausal status determined locally:
Estradiol (E2) must be above 54 pg/mL (or above 198 pmol/L), measured within 14 days prior to randomization.
- 6.1.3. Age \geq 18 years
- 6.1.4. Performance Status – Eastern Cooperative Oncology Group (ECOG) 0-1 (see chart at end of section*)
- 6.1.5. Histologically confirmed invasive breast cancer:
 - Primary tumor greater than 2 cm diameter, measured by clinical examination and mammography or echography (cT2-4b)
 - Any nodal stage
 - No evidence of metastasis (M0)
- 6.1.6. Primary tumor must have ER and PgR $>50\%$ of the cells
- 6.1.7. Primary tumor must be HER2 negative (by IHC and/or ISH)
- 6.1.8. Hematopoietic status:
 - Absolute neutrophil count $\geq 1.5 \times 10^9/L$
 - Platelet count $\geq 100 \times 10^9/L$
 - Hemoglobin ≥ 9 g/dL
- 6.1.9. Hepatic status:
 - Serum total bilirubin $\leq 1.5 \times$ upper limit of normal (ULN). In the case of known Gilbert's syndrome, a higher serum total bilirubin ($< 2 \times$ ULN) is allowed
 - AST and ALT $\leq 2.5 \times$ ULN
 - Alkaline phosphatase $\leq 2.5 \times$ ULN
- 6.1.10. Renal status: Creatinine $\leq 1.5 \times$ ULN
- 6.1.11. Negative serum pregnancy test, within 2-weeks (preferably 7 days) prior to randomization. Pregnancy test has to be repeated before treatment start if treatment does not start within 15 days of the previous test.
- 6.1.12. The patient must be willing to use effective non-hormonal contraception (barrier method – condoms, diaphragm – also in conjunction with spermicidal jelly, or total abstinence) after the pregnancy test and up to surgery. Oral, injectable, or implant hormonal contraceptives or medicated IUD are not allowed within 2 months prior to randomization and during the trial.
- 6.1.13. Prior fertility treatment is allowed but must have been stopped at least 12 months before randomization

- 6.1.14. The patient has completed the baseline patient-reported symptoms questionnaire
- 6.1.15. Written Informed Consent (IC) must be signed and dated by the patient and the Investigator prior to randomization
- 6.1.16. The patient has been informed of and agrees to data transfer and handling, in accordance with national data protection guidelines
- 6.1.17. The patient accepts blood samples to be taken according to the schedule in section 17.4 for the determination of the primary endpoint

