11.1. Before randomization

- 11.1.1. Breast palpation with tumor measurement and nodal status – caliper or ruler measurements preferred
- 11.1.2. Bilateral mammography and breast ultrasound (mandatory)
- 11.1.3. Chest X-ray; not required in patients who have undergone a PET scan
- 11.1.4. Abdominal ultrasound or CT scan is required if alkaline phosphatase or AST is $>2.5 \times \text{ULN}$; not required in patients who have undergone a PET scan
- 11.1.5. Bone scan is required if alkaline phosphatase is $>2.5 \times \text{ULN}$ or if the patient has unexplained bone pain; not required in patients who have undergone a PET scan
- 11.1.6. Tumor measurements according to WHO criteria for determination of response (see section 10) by mammography and breast ultrasound
- 11.1.7. Physical examination, ECOG Performance Status, and body weight
- 11.1.8. Hematology: Hemoglobin, platelet count, white blood cell count including differential (absolute neutrophil count)
- 11.1.9. Blood chemistry: blood urea nitrogen, creatinine, alkaline phosphatase, AST and ALT, total bilirubin, calcium, urea, total cholesterol, LDL and HDL cholesterol, triglycerides
- 11.1.10. CEA and CA 15.3
- 11.1.11. Menopausal status
- 11.1.12. Serum pregnancy test; has to be repeated before treatment start, if treatment does not start within 15 days of the previous test
- 11.1.13. Medical history including details of malignancy: date of diagnosis, primary tumor type characteristics (histology, grade, stage)
- 11.1.14. The determination of the estradiol level is mandatory within 4 days prior to randomization in order to check eligibility,
- 11.1.15. Patient must complete baseline PRS questionnaire.

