15.2.5. Node negative disease at surgery

The percentage of patients with node-negative disease at surgery will be descriptively summarized by treatment arm. Two sided 90% CI for the difference in percentage of patients with node-negative disease between treatment arms will be assessed.

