3.4 PATIENT DEMOGRAPHICS AND BASELINE DISEASE AND PRIOR TREATMENT

Characteristics of the ITT population will be summarized overall and according to treatment assignment. Continuous variables are summarized descriptively (e.g., mean, SD, minimum, maximum, and interquartiles(IQR)). Categorical variables are summarized as N (%); for variables with unavailable (missing, unknown, not done) values, the default approach is to list the number of unknowns as a category but calculate percentages excluding these unknowns from the denominator.

- Stratification factors (as analyzed)
- Patient:
 - Age at randomization
 - BMI at randomization
 - ECOG Performance status at randomization
 - Smoking status/history
 - Oral contraceptive use
 - Centrally assessed baseline E2 levels)
 - Baseline AE/symptoms, comorbidity history
- Pre-treatment Disease characteristics:
 - Tumor size or tumor lesion (via WHO criteria): product of maximum diameter (MD) and largest perpendicular diameter (LPD) of target lesions at baseline), multiple assessments (clinical, mammography, ultrasound)
 - Grade (centrally assess via core biopsy)
 - Histologic type (ductal, lobular, not determinable)
 - ER, PgR status, Allred score, and Her2 status of core biopsy
 - Clinical Nodal status
 - Ki67 label index (%)
 - Baseline CEA, CA15-3: CEA (carcinoembryonic antigen) and CA15-3 (breast cancer associated antigen)
- Prior Treatment (Hform):
 - Type of prior endocrine therapies: SERM, AI and GnRH/LHRH agonist (eligibility exclusions for any endocrine Rx taken within 12 months or oral contraceptive use within 2 months of rando), mainly to confirm not taken it.
- Tables
 - Characteristics, overall ITT population and by treatment assignment

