3.7 POST-TREATMENT SURGERY & PATHOLOGY

Centrally pathology assessment based on surgical specimens included histology type, tumor size, Ki67 level, ER status, ER Allred score, PgR status, PgR Allred score, Her2 status as measured by IHC or FISH, vessel invasion, LN status, and PEPI score (defined as in section 2.3.2)

Table of CPR pathological characteristics, overall and according to treatment assignments.

- Ki67 and ER Allred score data: baseline, post neoadjuvant/surgery data and percent change from baseline will be summarized, difference with 90%CI
- Node negative disease at surgery: percent of patients with node-negative disease is summarized overall, by treatment arms, difference between arms using exact binominal 90% CI

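### Node-negative disease at surgery is compared only as a crude difference, leaving collected baseline clinical nodal status unused; the cost is some precision and interpretability, not bias (minor)

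*SAP*

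**What the plan says.** The analysis is described in three places, each as an unadjusted comparison:

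- Protocol 15.2.5: "Two sided 90% CI for the difference in percentage of patients with node-negative disease between treatment arms will be assessed".
- SAP 2.2.6: "The percentage of patients with node-negative disease at surgery will be descriptively summarized by treatment arm", followed by "Two sided 90% CI for the difference in percentage of patients with node-negative disease between treatment arms will be reported".
- SAP 3.7: "percent of patients with node-negative disease is summarized overall, by treatment arms, difference between arms using exact binominal 90% CI".

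None of the three names a baseline covariate or stratum, or plans a table of nodal status at entry against nodal status at surgery.

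The baseline value exists. Protocol 6.1 admits "Any nodal stage". Protocol 11.1 requires "Breast palpation with tumor measurement and nodal status" before randomization. SAP 3.4 lists "Clinical Nodal status" among the pre-treatment disease characteristics, and says of the baseline tables: "Characteristics of the ITT population will be summarized overall and according to treatment assignment". Randomization (Protocol 7.5) is stratified by age alone, with balancing by institution.

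Other surgical endpoints do use the baseline state. Ki67 is analysed as change from the diagnostic biopsy (SAP 2.2.4, 2.2.6). Breast-conserving surgery has a conversion analysis and a table of planned against performed surgery (Protocol 15.2.6; SAP 2.2.6 and 3.8).

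**The concern.** Two things are lost.

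The first is precision. If clinical nodal status at entry predicts pathological nodal status at surgery, part of the spread in the crude difference comes from how many node-positive patients each arm happened to receive. A stratified difference removes that part, using data already on file.

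The second is meaning. The population mixes patients who enter with and without palpable nodal involvement. A percentage node-negative at surgery pools those who were never clinically positive with those whose nodes cleared on treatment. Only the second group speaks to nodal response, and the planned output does not separate the two.

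**Working it through.** **The plan's own figure.** The documents give no rate, effect size or power for this endpoint. The only sample-size figure, 90% power with 23 per arm (Protocol 15.1.1), is for the primary log-rank test. Simulating from the table's percentages gives about 92-93% with events spread evenly within intervals or placed at visit times, so that figure is broadly reproduced. It has no bearing on nodal status.

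**Inputs.** From the documents: n = 25 per arm (SAP 1.3; final accrual was 51 in all) and a two-sided 90% interval, so z = 1.645. Assumed, because no document gives them:

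- q = share clinically node-positive (cN+) at entry, 0.3 to 0.7
- a = probability of node-negative at surgery if cN0
- b = the same if cN+

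**Formulas (no treatment effect, large-sample).**

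- Overall rate: p = (1−q)a + qb
- Crude half-width: 1.645 × √(2p(1−p)/25)
- Within-stratum variance: w = (1−q)a(1−a) + qb(1−b)
- Stratified half-width: 1.645 × √(2w/25)
- Share of variance explained by baseline status: 1 − w/[p(1−p)]

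**Worked case, q = 0.5, a = 0.7, b = 0.2.** p = 0.45 and p(1−p) = 0.2475, so the crude half-width is 1.645 × √0.0198 = 23.1 points. w = 0.5 × 0.21 + 0.5 × 0.16 = 0.185, so the stratified half-width is 1.645 × √0.0148 = 20.0 points. Share explained: 0.0625/0.2475 = 25%.

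**Range over q = 0.3, 0.5, 0.7 (points).**

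| a / b | Crude half-width | Stratified half-width | Reduction | Share explained |
|---|---|---|---|---|
| 0.5 / 0.4 | 23.0-23.2 | 22.9-23.1 | 0.1 | about 1% |
| 0.6 / 0.3 | 22.7-23.3 | 21.8-22.4 | about 1 | 8-9% |
| 0.7 / 0.2 | 22.2-23.1 | 19.5-20.5 | 2.6-3.1 | 21-25% |
| 0.75 / 0.10 | 21.2-23.1 | 16.1-18.5 | 4.6-5.7 | 36-43% |

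The formula treats stratum sizes as equal across arms, so it slightly flatters the stratified estimate. Simulating the Mantel-Haenszel difference with the Sato variance at 25 per arm gives similar half-widths: about 22, 20-21 and 16-19 points for the last three rows. When baseline status is nearly uninformative there is a loss of about 0.2 points. Coverage is 88-89%, the same as for the crude Wald interval. Both estimators are unbiased in simulation.

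**Chance imbalance.** The SD of the between-arm difference in cN+ share is √(2q(1−q)/25): 13.0 points at q = 0.3 or 0.7, and 14.1 at q = 0.5. An imbalance of 20 points or more has a probability of 16-20%. It would shift the crude difference by 20 × (a−b): 2, 6, 10 and 13 points for the four rows.

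**The case against.** The strongest reply is that nothing here is an error. Randomization makes the crude difference unbiased, and its confidence interval already carries the variance from chance imbalance in nodal status. Protocol 15.2 declares the secondary analyses descriptive and largely underpowered. SAP 3.4 tabulates clinical nodal status by arm, so a reader would see an imbalance. The baseline value comes from palpation, an imperfect measure, so a wide gap between a and b cannot be presumed. All of this stands, and it keeps the point minor.

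It does not remove the point. The plan still reports a between-arm difference with an interval. A baseline table neither adjusts that estimate nor shows which patients changed nodal status.

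A second objection is sparse data. With about 12 cN+ patients per arm and a 10% rate, roughly one event is expected per arm in that stratum. The simulated coverage of 88-89%, equal to that of the crude Wald interval, answers this for a two-stratum analysis.

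A third is timing. SAP 2.2.5 and 2.2.6 already record results and analyses dropped because of them, so naming a new main comparison now would be post hoc. This stands: the stratified estimate belongs beside the planned one and should not replace it.

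**Conclusion.** A minor point of precision and interpretation. On the assumptions shown, stratifying shortens a 90% half-width of about 21-23 points by anything from nothing to about 5 points. Which applies depends on the cN+ share and on how well palpated status predicts surgical status; neither is in the documents. The interpretive gap does not depend on those assumptions: the planned output cannot tell patients who stayed node-negative from those whose nodes cleared.

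A reader might go further and infer that baseline imbalance dominates this comparison, that surgical nodal status depends mainly on nodal status at entry, or that the crude difference confounds drug effect with case mix. The documents do not support any of these. The crude estimate is unbiased, and even in the most favourable row of the table at least 57% of the variance is ordinary within-stratum binomial noise, which stratification cannot remove.

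**What to change.** In SAP 2.2.6 and 3.7:

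1. Keep the crude difference with its exact 90% CI as planned.
2. Beside it, labelled supplementary, add a Mantel-Haenszel risk difference stratified by baseline clinical nodal status (two strata only, cN0 and cN+), with a 90% CI from the Sato variance. State both interval methods in a footnote, since one is exact and the other large-sample, so a difference in width is not only the effect of adjustment.
3. Add a per-arm cross-tabulation of baseline clinical by surgical nodal status, parallel to the planned-versus-performed table for breast-conserving surgery. This is the more useful addition, as it needs no model.

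The cost is a few lines of code and text, with no new data. The drawbacks are a negligible loss of precision if palpated status proves uninformative, and the post hoc label that the SAP's timing requires.

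A separate matter to settle before building the table: SAP 2.2.4 defines node-negative as nodes assessed minus positive nodes equal to zero, which read literally selects patients whose examined nodes are all positive. The table should count patients with zero positive nodes.
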